2.2 Secondary Objectives

1. To determine the MRD-negative rate after ASCT
2. To evaluate the toxicity, response rate, PFS, and OS of IRD consolidation
3. To collect pilot data to compare toxicity, response rate, PFS, OS, and the rate of MRD-positive to MRD-negative conversion between the two maintenance arms
4. To evaluate the association of PFS and OS with MRD-negativity and MRD-positivity prior to consolidation and after 4 cycles of IRD consolidation

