5.0 TREATMENT PLAN

5.1 Overview

In general, patients will provide informed consent prior to ASCT. However, patients may be allowed to provide informed consent following ASCT, determined on a case-by-case basis by the PI. In this event, any of the assessments required prior to ASCT not performed for SOC will not be required.

Patients will undergo standard of care ASCT with conditioning regimen determined by the treating physician per institutional guidelines. The ASCT is not considered part of this study. Consolidation therapy will begin on between Day 80 and Day 120 following ASCT and will consist of four 28-day cycles of IRD (ixazomib, lenalidomide, & dexamethasone). Barring dose modifications for toxicity, 4 mg of ixazomib and 40 mg of dexamethasone will be administered on Days 1, 8, and 15, and 15 mg of lenalidomide will be administered on daily on Days 1-21.

Following completion of consolidation therapy, patients will undergo restaging and will be randomized on a 1:1 basis to maintenance therapy with ixazomib or lenalidomide. Patients will be stratified based on MRD status at restaging (MRD-positive v. MRD-negative). Patients who discontinue either ixazomib or lenalidomide during the consolidation phase due to toxicity will not be randomized. They will be preferentially enrolled on the opposing arm.

Barring dose modifications for toxicity, ixazomib maintenance will consist of 4 mg administered on Days 1, 8 and 15 of each 28-day cycle, and lenalidomide maintenance will consist of 10 mg daily on Days 1-28 for the first three 28-day cycles and 15 mg daily for all further cycles. Maintenance therapy with either ixazomib or lenalidomide will continue until the patient experiences disease progression or unacceptable toxicity.

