5.3.2 Ixazomib Administration

Ixazomib will be prescribed only to eligible patients under the supervision of the investigator or identified sub-investigator(s). Ixazomib will be administered on Days 1, 8, and 15 of a 28-day cycle at a starting dose of 4 mg. Sufficient quantity of drug for one cycle of therapy will be prescribed to the patient in Cycles 1-3 of maintenance therapy, and for three cycles of therapy in Cycles 4+.

Patients should be monitored for toxicity, as necessary, and doses of ixazomib should be modified as needed to accommodate patient tolerance to treatment; this may include symptomatic treatment, dose interruptions, and adjustments of ixazomib dose (see Section 6.0). Once ixazomib is reduced for toxicity, no dose re-escalation is permitted.

Ixazomib should be taken on an empty stomach (no food or drink), at least 1 hour before or 2 hours after a meal. Patients should be instructed to swallow ixazomib capsules whole and not to break, chew, or open the capsules. Each capsule should be swallowed separately with a sip of water. A total of approximately 8 ounces (240 mL) of water should be taken with the capsules.

Ixazomib should be taken at the same time each day. Missed doses can be taken as soon as the patient remembers if the next scheduled dose is 72 hours or more away. A double dose should not be taken to make up for a missed dose. Patients who vomit a dose after ingestion will not receive an additional dose, but should resume dosing at the time of the next scheduled dose.

If ixazomib maintenance is discontinued, crossover to the lenalidomide maintenance arm can occur if permission is granted by the Principal Investigator. Patients who crossover will continue to be followed per all protocol guidelines.

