8.0 STUDY CALENDAR

Please note that all assessments allow a window of +/-3 days for scheduling issues.

	Screening		Consolidation ³			Restaging ⁴	Maintenance ⁵			EOS ⁷	F/U ⁸
	Prior to ASCT ¹	Prior to beginning consolidation ²	D1	D8	D15		D1	D8	D15		
Informed consent	X										
H&P, ECOG PS, plasmacytoma assessment	X	X	X ¹³			X	X ^{13,14}			X	X ¹⁵
CBC & CMP	X		X ¹³		X ⁶	X	X ^{13,14}			X	
SPEP and immunofixation	X	X	X ¹³			X	X ^{13,14}			X	
24h urine for total protein, UPEP, and immunofixation ⁹	X	X	X ¹³			X	X ^{13,14}			X	
Serum-free light chains & β2 microglobulin	X	X	X ¹³			X	X ^{13,14}			X	
Quantitative immunoglobulins (IgA, IgG, IgM)	X	X	X ¹³			X	X ^{13,14}			X	
Serum βhCG ¹⁰	X	X	X				X			X	
Bone marrow biopsy and aspirate ¹¹	X	X				X	X ¹⁶				
Central labs ¹² (MRD Analysis)		X				X	X ¹⁶				
Central labs ¹² (Hevylite)	X		X ¹³			X	X ^{13,14}			X	
Central labs ¹⁸ (Sub-study)		X ¹⁸					X ¹⁸				
Ixazomib			X	X	X		X	X	X		
Lenalidomide			Days 1-21				Days 1-28				
Dexamethasone			X	X	X						
Administration Questionnaire ¹⁷			X				X				
Adverse events assessment			X ----- X								

1. Day -60 to Day -2

2. Day +80 to Day +120; to occur within 28 days prior to C1D1 of consolidation

3. 4 28-day cycles

4. Prior to beginning maintenance (approx. Day +192 to Day +232); to occur within 28 days after completing C4 of consolidation and within 28 days prior to C1D1 of maintenance

5. 28-day cycles; continued until progression or unacceptable toxicity

6. Cycles 1-2 only

7. Within 30 days of last dose of study drug(s)

8. Every 3 months for 18 months

9. Repeat 24h urine only required for patients with ≥ 200 mg/24h of M-protein at screening

10. Women of childbearing potential only; 2 negative tests are required within 14 days before study drug dosing on C1D1 of consolidation

11. Bone marrow aspirate and core biopsy – differential required; Cytogenetics, and fluorescent *in situ* hybridization (FISH) studies performed per institutional guidelines.

12. See Section 9.0

13. Not required on C1D1 if screening/restaging visit occurred within 28 days prior

14. C1-C4 then every 3 cycles thereafter (i.e., C7, C10, C13 ...)

15. A telephone call to assess OS and PFS can be made in lieu of a physical exam

16. Cycle 13 for all patients. Cycle 25 and 37 also required for patients in suspected or confirmed CR/sCR at that time.

17. See Appendix D. Patient to complete following each cycle of study treatment (consolidation and maintenance).

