11.10 Timeframe for Reporting Required Events

Adverse events will be collected from first dose of study treatment through the end of study visit.

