15.3 Data Analysis

For the analysis of consolidation therapy, the data for safety analysis will include these patients who have at least 1 dose of IRD consolidation therapy, while the data for efficacy analysis will include patients who complete 4 cycles therapy. Demographic and clinical characteristics of the sample, as well as adverse events, complications and loss to follow-up will be summarized using descriptive statistics. The change of MRD-negative rates for pre- and post-consolidation therapy will be described using contingency table and compared by McNemar test. The incidences of mortality, progression, relapse, as well as tumor response (complete response and overall) and their 95% confidence intervals following consolidation therapy will also be calculated.

Data analysis for maintenance portion will be performed following the intent-to-treat (ITT) principle. The balance of demographic and baseline clinical characteristics between two arms will be compared using t-test, Mann-Whitney rank-sum test, or Chi-square test as appropriate. The distributions of responses and adverse events across two arms will be summarized using contingency tables and compared by 2-sample Chi-square test or Fisher's exact test. Contingency table and Fisher's exact test will also be used to assess the between-arms difference for the rates of conversion from MRD-positive to MRD-negative. Chi-square test will be used to compare the distribution of responses, and Kaplan-Meier curves with log rank tests will be used to compare PFS and OS.

Overall survival (OS) will be defined as time from ASCT to death due to any causes, and survivors will be censored at withdrawal or study closeout. Progression-free survival (PFS) will be defined as time from ASCT to progression, relapse, or death, whichever occurs first, and those event-free survivors will be censored at withdrawal or study closeout. The between-arm differences in OS and PFS will be described using Kaplan-Meier product limit estimator and compared by log-rank tests. Kaplan-Meier curves will also be used to describe the association between MRD status (both prior to and after consolidation therapy) and OS or PFS, and proportional hazards Cox models will be used to control the potential confounding effects of other patient and clinical characteristics.

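### Maintenance adverse events are to be compared as crude proportions, although each patient's collection window depends on time on study drug, which can differ by arm

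*Combined protocol and SAP*

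**What the plan says.** Comparing toxicity is part of a secondary objective (Section 2.2): "To collect pilot data to compare toxicity, response rate, PFS, OS, and the rate of MRD-positive to MRD-negative conversion between the two maintenance arms". Section 1.4.1 also hypothesises that ixazomib maintenance will be well tolerated.

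Section 15.3 gives the method: "The distributions of responses and adverse events across two arms will be summarized using contingency tables and compared by 2-sample Chi-square test", with Fisher's exact test as alternative. The governing principle there is: "Data analysis for maintenance portion will be performed following the intent-to-treat (ITT) principle". Kaplan-Meier curves and log-rank tests are planned for PFS and OS only.

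Three other provisions fix how long a patient is observed for AEs:

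- Section 5.1: "Maintenance therapy with either ixazomib or lenalidomide will continue until the patient experiences disease progression or unacceptable toxicity".
- Section 11.10: "Adverse events will be collected from first dose of study treatment through the end of study visit".
- Section 8.0, calendar footnote 7: the end-of-study visit falls no later than 30 days from the last dose of study drug.

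Section 5.3.2 adds: "If ixazomib maintenance is discontinued, crossover to the lenalidomide maintenance arm can occur if permission is granted by the Principal Investigator". Section 5.3.3 allows the reverse switch. The documents contain no person-time rate, time-to-first-AE analysis, common fixed window or exposure summary by arm.

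**The concern.** A chi-square test on the share of patients with an event compares like with like only if both arms are observed for similar lengths of time. Here the window closes shortly after the last dose, and time on drug is itself an outcome of treatment. If one drug is stopped sooner, its patients contribute fewer months in which an AE can be recorded. Its crude share is then lower at the same monthly risk, and the p-value mixes toxicity with duration.

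At stake is how the toxicity comparison between ixazomib and lenalidomide is read. Section 1.4 intends it to feed the design of a phase III trial. The primary endpoint is not touched.

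**Working it through.** **Inputs from the documents.** 110 patients per arm and a lenalidomide event rate of about 54% at 5 years (15.1); event rates of 13% and 25% at 1 and 2 years, and a hazard ratio (HR) of 1.3 (15.4); accrual of about 3 years (15.1); an analysis at Year 6 (15.4).

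**Assumptions, not in the documents.** AE hazard h of 2% or 3% per month, equal in both arms; non-progression stopping s of 1%, 2% or 3% per month; constant hazards; two-sided 5% level; no crossover. The cited event rate is read as the rate of leaving drug through progression. Entry is uniform over 36 months with a cut at month 72, so potential time on maintenance is 36 to 72 months; the lag from entry to maintenance is ignored.

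**Step 1: the plan's own figures.** Under proportional hazards the event rate becomes 1 − (1 − p)^1.3.

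- 13% becomes 16.6% (+3.6 points; the plan says about 3).
- 25% becomes 31.2% (+6.2; the plan says about 6).
- 54% becomes 63.6% (+9.6; the plan says 10).

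These agree closely enough to use.

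**Step 2: progression hazard.** λ = −ln(0.46)/60 = 0.0129 per month.

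**Step 3: crude share at equal AE risk, with no stop counted as an AE.** With μ the total stopping hazard and k = h + μ, the share with an AE by time T is (h/k)(1 − e^(−kT)), averaged over T from 36 to 72. The average of e^(−kT) is (e^(−36k) − e^(−72k))/(36k).

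Example with h = 0.02 and stopping 3% v 1%:

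- Earlier-stopping arm: μ = 0.0429, k = 0.0629, share = 0.318 × (1 − 0.041) = 30.5%.
- Other arm: μ = 0.0229, k = 0.0429, share = 0.466 × (1 − 0.108) = 41.5%.

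| Difference between arms | Mean months on drug | Crude share, h = 2% | Crude share, h = 3% | Chi-square falsely significant |
|---|---|---|---|---|
| Progression HR 1.3 only, s = 1% in both | 28.2 v 30.6 | 38.9% v 41.5% | 49.9% v 52.9% | about 7% |
| s = 2% v 1% | 24.9 v 30.6 | 35.3% v 41.5% | 45.7% v 52.9% | 15–19% |
| s = 3% v 1% | 20.8 v 30.6 | 30.5% v 41.5% | 40.1% v 52.9% | 40–48% |

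If the arms differ only by HR 1.3 and there is no other stopping, the gap is 3.5 points (8% false significance) at h = 2% and 4.0 points (9%) at h = 3%. With a fixed 60-month window and h from 0.5% to 4%, the HR 1.3 gap runs from 1.6 to 4.3 points. In simulated trials under these settings, a test of the rate ratio per person-month rejects in about 5%.

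**Step 4: masking.** Take a fixed 60-month window and give the earlier-stopping arm 1.5 times the AE hazard (3% v 2% per month), with HR 1.3 plus extra stopping of 1% or 2% per month. Its crude share is 51.0% or 44.1%, against 52.3% in the other arm. At three times the hazard, with 1% extra stopping, it still shows more AEs (68.7% v 52.3%).

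**Step 5: stops that are AEs.** If every non-progression stop is a counted AE, the AE hazard becomes h + s and only λ ends observation without an AE.

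- Stopping 2% v 1%: shares are 71% v 62% (h = 2%) or 76% v 71% (h = 3%).
- Stopping 3% v 1%: shares are 76% v 62% or 80% v 71%.

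The earlier-stopping arm now looks worse. The two effects cancel when about 43–57% of the stops are counted AEs.

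**Step 6: does cumulative incidence remove the gap?** With end of treatment as a competing event, cumulative incidence follows the Step 3 formula at fixed T. At 24 months, h = 2% and stopping 3% v 1%, it gives 24.8% v 30.0%. The gap is smaller but still there.

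**The case against.** A reader might infer that the drug patients cannot tolerate will get the better AE table. The documents do not support that. Section 5.1 names unacceptable toxicity as the non-progression reason for ending maintenance, and Section 5.7 lists AEs among the reasons for removal. Such a stop is an AE inside the collection window and enters the table; Step 5 shows that the direction can then reverse. The downward bias needs stops that are mostly progression or non-AE, or an AE category other than the one that caused the stop.

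Three further points stand in part:

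- Crossover patients continue to be followed under the protocol, and the end-of-study visit is tied to the last dose of study drug. Stopping the assigned drug therefore need not close the window. If later events are counted by randomised arm, the bias can shrink or reverse. The plan does not say how they are counted, so crossover does not make the crude comparison safe.
- Early events are little affected. Section 6.5.4 places most rash in the first 3 cycles. The any-AE comparison is near its ceiling, with 98% and 94% in the pooled studies of Tables 1-2 and 1-3.
- The larger false-positive rates come from assumed stopping gaps. On the one between-arm difference the plan supplies, the distortion is small.

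The maintenance comparison is also pilot work, and no stopping rule uses an AE p-value. That limits the consequence. It does not justify a test that ignores exposure.

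**Conclusion.** The point holds as a conditional weakness. Section 15.3 tests AE proportions over windows that depend on time on drug, and nothing in the documents adjusts for it. If the arms differ only by HR 1.3, expect a spurious gap of about 3 points and 7–8% false significance (at most 4 points and 9% in the Year-6 settings above). The figures of 15–19% and 40–48% apply only if non-progression, non-AE stopping is 2% v 1% or 3% v 1% per month with equal AE risk. They are illustrations and do not forecast this trial. The documents give no AE hazard or discontinuation rate and no ground for expecting one particular arm to stop sooner. All figures assume constant hazards and no crossover. The change is a cheap improvement to a secondary, pilot comparison.

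**What to change.** In Section 15.3, make the between-arm AE comparison the rate of first events per patient-year on maintenance, as a rate ratio with 95% CI. Report it with duration of exposure by arm. Split it by period, for example the first 3 cycles and later, because the hazard may not be constant: rash tends to come early, and the planned lenalidomide dose changes after cycle 3. State whether events and time after crossover are both counted or both left out, so that numerator and denominator match.

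Keep the crude contingency table as description, without a p-value. Cumulative incidence at 12 and 24 months with end of treatment as a competing event may be shown beside exposure, also as description only, because it still reflects earlier stopping.

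The cost is SAP wording. Section 10.0 already has a Study Drug Dosing Form each cycle and continuous AE recording, so no visit, sample or patient is added. The downsides are that AE onset dates must be complete and that the rate ratio assumes a roughly constant hazard within each period.

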1.4.1 Hypotheses

- Consolidation with 4 cycles of IRD will be well tolerated and will result in \geq 15% improvement in MRD-negative rate
- MRD-negativity after 4 cycles of IRD consolidation will be associated with an improved PFS and OS
- Maintenance therapy with ixazomib will be well tolerated and will be similar in response rate, PFS, OS, and MRD-positive to MRD-negative conversion rate to maintenance therapy with lenalidomide.

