5.3 Maintenance Therapy

5.3.1 Randomization

Following completion of consolidation therapy, patients will undergo restaging and will be randomized on a 1:1 basis to maintenance therapy with ixazomib (Arm1) or lenalidomide (Arm2). Patients will be stratified based on MRD status at restaging (MRD-positive vs. MRD-negative). To better ensure the balance of patient characteristics across two arms, treatment assignment will be implemented in small blocks of 4 to 6 patients. The randomization table will be uploaded in our REDCap system. Randomization will occur via an online form with entry of the patient ID number and stratum information. Once all information is entered, randomization is carried out via a submit button through REDCap. The randomization scheme will be created using a formal probability model implemented in SAS (version 9.3 or higher).

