15.1 Determination of Sample Size

A power analysis was performed for the primary objective. The smallest increase in MRD-negative rate after four cycles of IRD that would warrant further investigation is 10%, with a result of $\leq 9\%$ being considered ineffective. Based on a meta-analysis of five prior studies in this population, the expected MRD-negative rate at Day 100 post-transplant is ~50%. If the true rate of MRD-negative is 40-60% at the Day 100 post-transplant visit, 220 evaluable patients will detect a 10% improvement in MRD-negative rate with 90% power at 1-sided 0.05 alpha. Due to highly varied data of baseline MRD (i.e., 5 published studies showed MRD-negative rates ranged from 8% to 62%) as well as the lack of pilot information for the association over time, we currently choose a rather conservative estimation and the sample size is estimated using non-paired design instead. However, an interim analysis will be performed when ~50 patients are randomized to maintenance arms, and sample size adjustment will then be made if needed (see details below for interim analysis).

The randomized maintenance portion of the study will provide pilot data that will be used to design future studies. Although the study was not powered to show non-inferiority or superiority of either of the two maintenance arms, the designed sample size (n=110 evaluable patients/arm) will provide us a reasonable power for our hypothesis that "Maintenance therapy with ixazomib will be well tolerated and will be similar in response rate, PFS, OS, and MRD-positive to MRD-negative conversion rate to maintenance therapy with lenalidomide". Taking PFS as an example, the recent meta-analysis of lenalidomide versus placebo/observation showed that the 5-year cumulative incidence of events (PD or 2nd-line treatment) was ~54%. [29] The figure below illustrates the statistical power to show non-inferiority given the "true" difference of event rates (e.g., death or recurrence or treatment failure) between the ixazomib arm (experimental group) and lenalidomide arm (control group). With a non-inferiority margin of 10% in 5-year PFS (or equivalently a hazard ratio (HR) of 1.3), for example, the designed sample size would allow 80% power to claim non-inferiority when a slightly better PFS is observed in the ixazomib arm.

This power analysis was based on a simulation study where

- the true rate in the experimental treatment (ixazomib) varied from 45% to 65%;

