15.2 Randomization and Stratification

Following initial treatment with IRD consolidation therapy, patients will be randomized to a pilot portion of the study evaluating ixazomib or lenalidomide as maintenance therapy.

Patients will be restaged following completion of consolidation treatment and will be randomized on a 1:1 basis to maintenance therapy with ixazomib or lenalidomide. Patients will be stratified based on MRD status at restaging (MRD-negative v. MRD-positive). For the purposes of randomization, if there are discrepant results from the Mayo Clinic MFC and the Adaptive ClonoSEQ MRD tests, the Adaptive ClonoSEQ results will be used for stratification. In the event that the Adaptive ClonoSEQ results are not available, the Mayo Clinic MFC results will be used for stratification, and vice versa.

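### The between-arm test of maintenance response (15.3) ignores category order, response at restaging and the MRD stratum, and so gives up precision

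*Combined protocol and SAP*

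**What the plan says.** The maintenance paragraph of section 15.3 states the response test twice. Responses and adverse events are to be tabulated by arm and "compared by 2-sample Chi-square test or Fisher's exact test"; a later sentence adds "Chi-square test will be used to compare the distribution of responses". Neither test uses the order of the categories or any stratum. The analysis set is everyone randomised: "Data analysis for maintenance portion will be performed following the intent-to-treat (ITT) principle". No time point or window for maintenance response is given.

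The unused information is in the plan. Section 12.1 grades response on the IMWG scale (sCR, CR, VGPR, PR, SD, PD). Section 15.2 says "Patients will be restaged following completion of consolidation treatment", and the study calendar (8.0) places that visit before maintenance begins. Randomisation is stratified by MRD status at restaging (5.3.1, 15.2).

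Secondary objective 3 (2.2) includes response among the pilot comparisons, and the third hypothesis (1.4.1) is that ixazomib maintenance "will be similar in response rate, PFS, OS" and MRD conversion to lenalidomide maintenance.

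**The concern.** Patients reach randomisation after induction, ASCT and four IRD cycles, so many will already hold a response. Under ITT all of them enter the response table, including those in the top category, who cannot improve. If response during maintenance partly repeats the restaging category, that spread is noise for the drug comparison, and a plain chi-square leaves it in. Ignoring category order loses a further, smaller amount.

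What is at stake is how much the pilot can say about response. These data are meant to help design a later trial (1.4, 15.1), and an imprecise comparison is a weak basis for that. The plan already conditions on baseline for MRD, by testing conversion from positive to negative, but not for response.

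**Working it through.** **Inputs from the documents.** 110 evaluable patients per arm (15.1); 1:1 allocation (15.2); ITT (15.3); lenalidomide PFS event rates of 13% at 1 year and 25% at 2 years (15.4).

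**Assumptions, not in the documents.** Two-sided alpha 0.05; restaging distributions CR/VGPR/PR/SD of 45/40/13/2, 30/50/17/3 and 60/30/8/2; one-category upgrades in 20% v 40% of patients below CR.

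**1. The plan's own figure.** No power is stated for response. The only maintenance figure is 80% for PFS non-inferiority with a 10-point margin. Power = Φ((0.10 − d)/SE − z₀.₉₀), with SE = √[p_C(1−p_C)/110 + p_T(1−p_T)/110] and d = p_T − p_C, averaged over control rates of 52-56%, gives 58% at d = 0, 79% at d = −0.04 and 83% at d = −0.05. The stated 80% fits a true advantage of 4-5 points. It says nothing about response.

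**2. Best response, hand check (45/40/13/2).** Each patient keeps the restaging category or rises by one.
- Final distribution at 20% upgrade: 53.0/34.6/10.8/1.6. At 40%: 61.0/29.2/8.6/1.2.
- Chi-square noncentrality λ = n Σ(p₁−p₂)²/(p₁+p₂) = 110 × (0.0064/1.14 + 0.002916/0.638 + 0.000484/0.194 + 0.000016/0.028) = 1.46. On 3 df (critical value 7.81) power is about 15%.
- Upgrade rate among patients below CR: 0.55 × 110 = 60.5 per arm; SE = √[(0.16 + 0.24)/60.5] = 0.0813; power = Φ(0.20/0.0813 − 1.96) = Φ(0.50) = 69%.

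**3. Best response, simulation (2,000 trials per setting).**

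| Restaging CR | Chi-square | Wilcoxon (order only) | van Elteren by restaging category | Upgrade rate below CR |
|---|---|---|---|---|
| 45% | 14% | 22% | 67% | 68% |
| 30% | 21% | 30% | 76% | 78% |
| 60% | 11% | 16% | 54% | 55% |

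Order alone adds 5-9 points. Nearly all the rest comes from using the restaging response.

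**4. Dependence on carry-over.** A second assumed distribution has five categories (5/10/35/20/30, worst to best).
- Keep-or-rise-by-one, 20% v 40%: chi-square 11%, van Elteren 77%; loss 1 − 0.110/0.774 = 86%. A three-category version gives 15% v 62%, a loss of 75%.
- Correlated latent responses, correlation 0.3, shift 0.4 SD: 55% v 80%; loss 1 − 0.549/0.795 = 31%.
- Correlation 0.85, shift 0.2 SD: 16% v 59%; loss 1 − 0.163/0.588 = 72%.

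Over correlations of 0.3-0.85 and shifts of 0.2-0.4 SD, the loss ranges from 31% to 72%.

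**5. Progressions counted at a fixed visit.** The model of step 3, with 13% or 25% of patients in both arms moved to PD (the 15.4 event rates, used only for scale; equality between arms is assumed).

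| Moved to PD | Chi-square | van Elteren |
|---|---|---|
| 0% | 10-22% | 54-79% |
| 13% | 7-16% | 20-41% |
| 25% | 6-14% | 10-22% |

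Progression puts extreme ranks into every stratum, including patients in CR, and swamps the upgrade signal in the ordered test. The upgrade rate among patients below CR, with progressed patients counted as not improved, kept 39-71% power over the two progression settings.

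**6. Type I error.** It was 4-6% throughout. The planned test is valid.

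**The case against.** A reader might infer three stronger things, and the documents support none of them.

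- **That most of the power is lost, as a fact.** The documents give no restaging distribution, upgrade rate, correlation or target difference. The largest losses come from a model in which patients can only stay or rise by one category, so baseline explains nearly everything. With weak or moderate correlation the loss is roughly a third to a half.
- **That a non-significant chi-square will be reported as similarity.** No section says so. Section 15.1 says the study was not powered for non-inferiority or superiority of either maintenance arm, and illustrates similarity through a confidence bound against a margin, for PFS.
- **That the comparison is biased.** Patients are "randomized on a 1:1 basis to maintenance therapy with ixazomib or lenalidomide", so restaging response is balanced on average.

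Other points on that side also stand. The assumed 20% v 40% contrast is a difference of only 11, 14 or 8 points in the whole randomised population (0.20 × 0.55, 0.70 or 0.40). At 20% v 30% the van Elteren test itself has only about 25% power with 45% in CR. The simulations in steps 2, 3 and 5 put CR at the top and do not model MRD strata, so they illustrate the recommended analysis without giving its exact power. The MRD-conversion comparison already covers part of the question. Best response hides later loss of response and depends on time under observation.

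None of this restores the unused information. The stratified test had more power than chi-square in every effect scenario above, and no other section adjusts maintenance response for restaging status.

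**Conclusion.** The point holds as a loss of precision. The planned test leaves out category order, restaging response and the MRD stratum. For best response the loss was substantial in every scenario run: 31-72% of the power under correlated latent responses and 75-86% where response largely carries over from restaging. Which applies cannot be settled from the documents. The advantage of the ordered stratified test depends on best response being the endpoint, which 15.3 does not say, and is much smaller at a fixed visit with progressions counted. The upgrade proportion holds up better there and should be the lead measure.

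The consequence is limited by the pilot, secondary status of the comparison. The remedy is cheap, so the change should be made before the maintenance data are analysed.

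**What to change.** In section 15.3, replace the two chi-square/Fisher statements as they apply to maintenance response with:

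- **Main comparison.** The between-arm difference, with 95% CI, in the proportion of patients whose best response during maintenance, within a stated window, improves at least one category from restaging, among those not already in sCR at restaging, stratified by MRD status at randomisation. State the window and how patients without an assessment in it are counted.
- **Supporting test.** An ordered comparison of best response (van Elteren or proportional odds), stratified by restaging response with sparse SD and PR categories pooled, and adjusted for the MRD stratum.
- **Description.** Keep the raw response-by-arm table without making its chi-square the basis for inference.

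The cost is a paragraph of text and a little more analysis, with no new data. Pooling will probably be needed: at the assumed 2-3% in SD, that stratum holds about 4-7 of 220 patients (0.02 × 220 = 4.4; 0.03 × 220 = 6.6). Best response does not show later loss of response; PFS captures that and remains in the plan.
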